11.5.5 Secondary Analysis

Overall survival will be analyzed using Kaplan-Meier techniques. Tests of statistical significance between the arms will be carried out using the log-rank test. The 12-month survival rate will be estimated for each study arm based on the Kaplan-Meier estimates. A statistical test of significance will be carried out to compare the 12-month survival rates between the arms. This will be accomplished by pooling the standard errors of the 12-month OS rates and performing a Chi-Square test. Additional survival analyses and analysis of time from hospice referral to death will be conducted using Cox-proportional hazards models. Thirty-day readmissions will be analyzed using Poisson regression. Length of stay and adherence to clinical care will be analyzed using analysis of variance techniques. The frequencies and proportions of subjects referred to Supportive Oncology services will be calculated, alongside corresponding 95% confidence intervals estimated using the Clopper-Pearson method.

The following models will be estimated for each of the six multi-scale measures, thirteen single-item measures, and one average overall standardized score: Linear mixed models for repeated-measures will be used to analyze subject-level satisfaction as assessed through the derived endpoints of the EORTC IL109 customized questionnaire. Fixed factors included in the models will be treatment arm, sampling time (T1 and T2) and the treatment by time interaction. A random factor for subject will be included in the models to account for repeated observations on the same subject. For single-item measures, mixed-effects models for repeated ordinal outcomes will be estimated for the thirteen single-item measures using ordinal logistic regression. The response outcome may be treated as a 5-level raw score or a collapsed version (e.g., 2-level factor as raw scores 1-3 versus 4-5) as appropriate. Similarly, fixed factors included in the models will be treatment arm, sampling time (T1 and T2) and the treatment by time interaction, and a random factor for subject will be included in the models to account for repeated observations on the same subject.

Using the models described above, univariate and multivariable modeling will be conducted to identify baseline prognostic factors and to estimate adjusted between-arm treatment effects. All models will be stratified including the stratification factors used in the randomization. Univariate models will be used to identify baseline factors (including subject demographic, socioeconomic, and clinical characteristics) that are individually prognostic. Statistically significant factors identified from the univariate models will then be jointly included in a multivariable model. Backwards elimination will be used to identify baseline factors that are independently prognostic. If it is determined that the sample sizes in some stratification strata are too sparse, then strata will be combined prior to analyses. This will result in a smaller number of strata, each with larger sample sizes.

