11.2 Sample Size

This study is designed with co-primary objectives to evaluate the acute care utilization and 6-month OS rate. Power and sample size calculations were primarily calculated based on the OS landmark objective. The overall type I error rate for this study is alpha = 0.05. Therefore, the co-primary endpoints were both powered at the 2-sided alpha = 0.025 significance level. We estimate that treatment with standard therapy results in median survival of 8 months. Assuming an exponential distribution, this corresponds to a 6-month survival rate of approximately 60%. Therefore, the primary OS objective of this study is designed to test the null hypothesis that the 6-month OS survival rate is \leq 60%. A total of 300 evaluable subjects enrolled in a one-to-one fashion will provide 80% power, assuming the true 6-month OS rate with Nurse Navigation is 80%. A total of 347 subjects may need to be enrolled to achieve 300 evaluable subjects. A 20% improvement in the 6-month OS rate is considered clinically relevant. This sample size will also provide at least 93% power to detect a 20% reduction in acute care visits (assuming there will be 6 acute care utilization visits per year in the control arm).

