11.3.3 Definition of Exploratory Endpoint

Time to initiation of systemic therapy will be calculated as the difference (in days) between the dates of enrollment and initiation of systemic therapy (this difference is 0 when treatment initiation occurs on the date of enrollment). A binary variable indicating if the time to initiation of systemic therapy is less than 0 (i.e., systemic therapy was initiated prior to date of enrollment) will be determined for each subject.

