11.5.4 Primary Analysis

The frequency and proportion of subjects alive at 6 months or better will be calculated for each study arm. Corresponding 95% confidence intervals will be estimated using the Clopper-Pearson method. A

two-sided test for binomial proportions will be carried out, testing the null hypothesis that there is no difference in the OS6 rate between the arms.

Poisson regression analyses will be used to analyze acute care utilization visits. Treatment arm will be included in the model as the primary covariate and an asymptotic test of significance will be carried out to compare acute care utilization between the arms.

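### The co-primary acute care model names no covariate but arm and leaves the role of the randomisation factors unclear; separately, adjusted arm effects use covariates selected from the outcome data

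*Combined protocol and SAP*

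**What the plan says.** Section 11.5.4 (Primary Analysis) analyses ACU by Poisson regression with an asymptotic test of the arm effect. On the content of the model it says: "Treatment arm will be included in the model as the primary covariate". No other term, offset or variance estimator is named. Section 11.3.1 defines the endpoint as a visit count put on an annual basis, and section 5.4 collects ACU until the subject goes off intervention, so follow-up differs between subjects.

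Section 11.5.5 (Secondary Analysis) reuses the models set out before it "to identify baseline prognostic factors and to estimate adjusted between-arm treatment effects". It says every model is to be stratified by the randomisation factors, which section 4.1 gives as COVID-19 study period and disease diagnosis. Sparse strata may be merged, but no rule for merging is given. Covariates are chosen in two steps. First, "Statistically significant factors identified from the univariate models will then be jointly included in a multivariable model". Backward elimination then follows. No significance threshold or closed list of candidates is given.

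The baseline data are available. The study calendar and section 7.1 collect date of birth, sex, race, live-in caregiver, income, insurance, education, BMI, diabetes and pre-existing conditions. Section 11.3.3 adds "A binary variable indicating if the time to initiation of systemic therapy is less than 0", meaning treatment had begun before randomisation.

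On size, section 11.2 states that "the co-primary endpoints were both powered at the 2-sided alpha = 0.025 significance level" and that "This sample size will also provide at least 93% power to detect a 20% reduction in acute care visits". The control rate behind that power figure is taken as 6 visits per year.

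**The concern.** There are two separate issues.

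- **The primary ACU model is not fully stated.** A co-primary test should have one fixed model. Here the randomisation factors may be in or out, and if they are in, the pooling of strata is open. Beyond those factors, no baseline variable is pre-specified, although insurance, caregiver support and treatment already under way could plausibly relate to unplanned visits. If they do, the estimate is less precise than the data allow.
- **One procedure serves two purposes.** Screening and elimination can suit a search for prognostic factors. Used for adjusted arm effects, they let each endpoint's own outcome data choose its covariates, so the set can differ between endpoints and is unknown in advance. The adjusted effects are then open to criticism as data-driven.

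**Working it through.** **1. The plan's own power.** Inputs from section 11.2: control rate 6 per year, rate ratio 0.80 (so 4.8 per year with navigation), two-sided alpha 0.025 (z = 2.2414). Assume one person-year each and no overdispersion.

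Power = Φ(|ln 0.8| / √((1/6 + 1/4.8)/n) − z), with |ln 0.8| = 0.2231 and 1/6 + 1/4.8 = 0.375.

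- n = 107 per arm (before re-estimation, section 11.5.8): 0.2231/0.0592 − 2.2414 = 1.528, power 93.7%.
- n = 150 per arm: 0.2231/0.0500 − 2.2414 = 2.221, power 98.7%.
- n = 79 per arm, alpha 0.05 (the 158-subject fallback in 11.5.8): 89.95%, against a stated 90%.

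The stated 93% matches 107 per arm and is a true lower bound at 150. The design figures therefore correspond to a pure Poisson model with one year per subject.

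**2. What covariates could add.** The documents give no dispersion and no mean exposure, so both are assumptions here. With dispersion k and mean exposure t years, the variance of the log rate ratio is (0.375/t + 2k)/n. If covariates explain a share R of the heterogeneity, k becomes k(1 − R). For k = 0.5, t = 1, n = 150:

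- Unadjusted: √(1.375/150) = 0.0957; 0.2231/0.0957 − 2.2414 = 0.089; power 53.6%.
- R = 0.3: √(1.075/150) = 0.0847; power 65.3%; variance cut 0.3/1.375 = 21.8%.

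| t (years) | k | Power unadjusted | R = 0.1 | R = 0.3 | Variance cut |
|---|---|---|---|---|---|
| 1 | 0 | 98.7% | 98.7% | 98.7% | 0 |
| 1 | 0.25 | 75.2% | 77.9% | 83.4% | 5.7-17.1% |
| 1 | 0.5 | 53.6% | 57.1% | 65.3% | 7.3-21.8% |
| 1 | 1 | 32.0% | 34.9% | 42.5% | 8.4-25.3% |
| 0.5 | 0 | 82.0% | 82.0% | 82.0% | 0 |
| 0.5 | 0.25 | 58.0% | 60.0% | 64.2% | 4.0-12.0% |
| 0.5 | 0.5 | 43.0% | 45.5% | 51.1% | 5.7-17.1% |
| 0.5 | 1 | 27.6% | 29.8% | 35.3% | 7.3-21.8% |

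**3. Variance estimator and selection, by simulation.** 600 trials per setting, 150 per arm, one year each, k = 0.5, 12 candidate covariates of which 3 are prognostic. Selection was a 0.05 univariate screen, then backward elimination, with arm always kept. The test is at 2.5%.

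| Analysis | Null rejection, R = 0.3 | Mean SE (null, R = 0.3) | Null rejection, R = 0.1 | Power, R = 0.3 | Power, R = 0.1 |
|---|---|---|---|---|---|
| Poisson SE, arm only | 24.8% | 0.0472 | 27.2% | not valid | not valid |
| Poisson SE, fixed list | 21.2% | 0.0475 | 26.0% | not valid | not valid |
| Robust SE, arm only | 2.0% | 0.0929 | 3.7% | 55.2% | 54.8% |
| Robust SE, fixed list | 3.8% | 0.0830 | 3.2% | 65.2% | 58.2% |
| Robust SE, selected | 4.3% | 0.0827 | 3.0% | 65.5% | 58.2% |

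The ordinary Poisson SE does not shrink with adjustment, and its test is invalid either way. With robust SEs the variance falls by 1 − 0.0830²/0.0929² = 20%. Selected and fixed lists cannot be told apart: the Monte Carlo SE near 4% is √(0.04 × 0.96/600) = 0.8 points. A separate check of stepwise selection in linear models (4,000 runs, nominal 5%) gave type I error of 4.6% and 5.8%, against 4.7% and 5.5% unadjusted.

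**4. Other assumptions.** With gamma heterogeneity 0.4, mean exposure 0.55 year, assumed covariate rate ratios of 1.25-1.4 plus diagnosis, and robust SEs, the variance went from 0.0185 to 0.0152 (1 − 0.0152/0.0185 = 18%) and power from 34% to 41%. With effects 40% weaker the variance cut was 4%. A further run with gamma 0.4 and roughly half a year of exposure gave variance cuts of about 5-14%, and power of 32% to 41%, or 35% to 39% with weaker covariates.

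**The case against.** A fair defence has several parts.

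- **A reader might infer that the ACU model contains arm only.** The text calls arm the primary covariate, not the sole one, and the stratification sentence in 11.5.5 may bring in study period and diagnosis. This stands. What remains is an ambiguity, and the 18% in step 4 counts diagnosis as new adjustment when it may already be planned.
- **A reader might infer that selection in 11.5.5 costs the primary test its precision.** It does not. That precision is settled by 11.5.4; the two issues are separate.
- **A reader might infer that the ACU rate ratio changes meaning with the covariates chosen.** In a randomised comparison with a log link, a constant rate ratio and follow-up unrelated to arm, it does not. A check with 2 million simulated subjects, a strong omitted covariate correlated with follow-up and a true ratio of 0.80 gave 0.801 unadjusted. Dependence on the covariate set is an issue for the hazard and ordinal-logit models.
- **A reader might infer that elimination could drop arm.** The text confines elimination to baseline factors and aims at arm effects, so arm should stay. One explicit sentence would settle it.
- **The gain is assumed.** This stands. It is zero under the design's own Poisson assumption, and no passage gives effect sizes for any covariate.
- **An unadjusted or strata-adjusted primary analysis is legitimate.** This also stands. It does not excuse leaving open which of the two is planned.

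**Conclusion.** The point holds as one of incomplete specification and possibly forgone precision. Section 11.5.4 does not say whether the randomisation factors enter the co-primary ACU model and uses no other collected baseline variable. Section 11.5.5 reports adjusted arm effects whose covariates are not fixed in advance.

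The size rests on assumed overdispersion, exposure and covariate strength: about 4-25% lower variance of the log rate ratio under overdispersion, and nothing without it. Some overdispersion is plausible, given several cancer types and unequal follow-up, but the documents do not quantify it. If it is present, ignoring it is the larger risk to this test, and covariates alone do not cure it. The documents and calculations do not support a claim that selection inflates type I error or loses power; the objection to it is lack of pre-specification. The change is worth making because it is cheap, but this is not a demonstrated failure of the primary analysis.

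**What to change.** In 11.5.4, state the primary ACU model in full:

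- visit count as outcome, with a log-exposure offset;
- arm, study period and diagnosis, with a fixed rule for combining sparse strata;
- a short fixed list of collected baseline covariates, for example age, sex, insurance, live-in caregiver, and systemic therapy started before randomisation, with categories defined;
- a robust variance or a negative binomial model. Under overdispersion, adjustment without this neither shrinks the reported SE nor gives a valid test.

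Report the unadjusted effect as supportive. In 11.5.5, use the same list for all adjusted arm effects, state that arm is always retained, and keep univariate screening and backward elimination for the prognostic-factor question only.

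The cost is SAP wording, settled before anyone choosing the list sees ACU results by arm. No new data are needed. Missing covariate values need a simple rule, such as a missing category. As main effects the model spends 1 + 5 degrees of freedom on the randomisation factors (two periods, six diagnosis groups), 4 on age, sex, caregiver and prior start of therapy, and one fewer than the number of insurance categories. That is small against 300 subjects.

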11.5.6 Exploratory Analysis

Descriptive statistics (including, but not limited to, mean and standard deviation, median and range, interquartile range) will be calculated to describe the distribution of time to initiation of systemic therapy. The frequency and proportion of subjects initiating treatment on study will be calculated for each study arm; corresponding 95% confidence intervals will be estimated using the Clopper-Pearson method and these proportions will be compared between the arms using Fisher's Exact tests.

The following will be performed in the subset of evaluable subjects initiating treatment on study only:

Time to initiation of systemic therapy will be compared between the arms using analysis of variance techniques. If the distribution is highly skewed, a log transformation may be performed.

Time to initiation of systemic therapy may be summarized as a categorical variable (e.g., time to treatment initiation is between 0 and 6 days versus 7+ days) based on the observed distribution in this subset of evaluable patients. Outcomes may be evaluated and compared within the ONN arm with regards to time to initiation of systemic therapy. Time from enrollment to initiation of systemic therapy may be assessed separately as both a continuous and categorical measure where appropriate. These analyses will be conducted on the primary and secondary endpoints as described above; time from enrollment to initiation of systemic therapy may be the comparison/covariate of interest.

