11.1.2 Enrollment Date

The date that the subject is randomized.

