11.4 Analysis Populations

The intent to treat (ITT) population will consist of all randomized subjects. This population will be used to summarize the CONSORT diagram, subject disposition, and baseline subject and disease

characteristics. The evaluable population will consist of all enrolled subjects who meet both of the following criteria:

- Receive at least one dose of standard of care systemic anti-cancer therapy on or after the enrollment date
- Die within six months of enrollment or otherwise are on study for at least 6 months.

The evaluable population will be used for the analyses of all primary, secondary, and exploratory endpoints and interim analyses. Select analyses of time to initiation of systemic therapy will be conducted on the subset of the evaluable population initiating systemic therapy on study only (Section 11.5.6). Additionally, an intervention-compliant population will be defined as all subjects in the evaluable population who meet all of the following criteria:

- Subjects received intervention they were randomized to:
 - Subjects randomized to the ONN arm who have at least one LPNP encounter within 2 weeks from randomization.
 - Subjects randomized to the control arm who do not have any LPNP encounters within 6 months from randomization.

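### In 11.5.6 the proportion initiating treatment on study is the complement of being on therapy before randomisation, so its between-arm Fisher test cannot be interpreted as an effect of navigation on starting therapy

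*Combined protocol and SAP*

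**What the plan says.** Five provisions combine.

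- **11.1.2** defines enrollment as "The date that the subject is randomized".
- **3.2 and 5.1** let a subject enroll up to 30 days after systemic therapy has begun, so some subjects are already on treatment when randomised.
- **11.3.3** sets time to initiation as the start date relative to enrollment, with a binary variable for a negative value, meaning that "systemic therapy was initiated prior to date of enrollment". It gives no value for a subject who never starts.
- **11.4** states "The evaluable population will be used for the analyses of all primary, secondary, and exploratory endpoints and interim analyses". Membership needs both "Receive at least one dose of standard of care systemic anti-cancer therapy on or after the enrollment date" and "Die within six months of enrollment or otherwise are on study for at least 6 months". The ITT population is kept for the CONSORT diagram, disposition and baseline tables.
- **11.5.6** states "The frequency and proportion of subjects initiating treatment on study will be calculated for each study arm", and that "these proportions will be compared between the arms" with Fisher's exact test. It names no other population for this step. It then compares time to initiation between arms by ANOVA, in evaluable subjects who began treatment on study.

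The timing objectives in 2.1.3 are to describe the distribution of time to initiation and to relate outcomes to it within the ONN arm. Neither is a between-arm comparison.

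**The concern.** A p-value comparing the arms on initiating treatment on study looks like a test of whether navigation gets patients onto therapy. Readers are likely to take it that way: 5.1 gives speeding up care as one of the navigator's aims, and 1.1.6 cites studies in which navigation shortened time to treatment.

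The population rule removes the subjects who would carry that information. A subject untreated at randomisation who never starts fails the first evaluability criterion and leaves both numerator and denominator. The subjects who remain differ only in whether they started before or after randomisation, and the earlier start is fixed before navigation can act. A significant result could then be reported as a navigation effect when it is mostly imbalance at entry. A null result could hide a real gain in uptake. The ANOVA shares part of the problem, because it conditions on having started after randomisation, which navigation may itself influence.

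**Working it through.** The plan gives no alpha, power, sample size or expected proportion for this test, so there is no figure to reproduce. The main result follows from the definitions; the arithmetic only shows its size.

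**Step 1: the identity.** Every evaluable subject has a dose on or after randomisation. The first dose therefore fell either before randomisation (time < 0) or on or after it (time ≥ 0), and no third category exists. Hence

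P(initiating on study | evaluable) = 1 − P(started before randomisation | evaluable).

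Among evaluable subjects untreated at randomisation, 100% initiate on study, in both arms, by construction.

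**Step 2: how an arm effect can still enter.** Let u be the share untreated at randomisation (equal in both arms) and s the probability that an untreated subject starts. If all prior starters receive a further dose and the six-month criterion removes no one,

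on-study share in the evaluable set = u·s / (u·s + 1 − u).

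If s is equal in both arms, the shares are equal. At s = 80% they are 76.2%, 54.5% and 34.8% for u = 80%, 60% and 40%. If s differs, the share moves only because never-starters leave the denominator at different rates.

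**Step 3: illustration.** The assumptions, none from the documents, are s = 95% (ONN) against 85% (control), u from 40% to 80%, and two-sided alpha 0.05. From the documents come 347 enrolled and 1:1 allocation, so about 173 per arm.

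| u | ONN share | Control share | Difference (points) |
|---|---|---|---|
| 40% | 0.38/0.98 = 38.8% | 0.34/0.94 = 36.2% | 2.6 |
| 50% | 0.475/0.975 = 48.7% | 0.425/0.925 = 45.9% | 2.8 |
| 60% | 0.57/0.97 = 58.8% | 0.51/0.91 = 56.0% | 2.7 |
| 80% | 0.76/0.96 = 79.2% | 0.68/0.88 = 77.3% | 1.9 |

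The true effect is 10 points in every row. By exact enumeration, with evaluable numbers per arm equal to 173 × (u·s + 1 − u), Fisher power is 7.0%, 7.4%, 6.9% and 6.1% down the table. A normal approximation at 150 per arm gives about 7% to 8%.

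**Step 4: direct comparison.** Among all randomised subjects untreated at enrollment, the contrast is the full 95% against 85%. With u = 60%, 173 × 0.60 ≈ 104 per arm, and exact Fisher power is 61%. With u = 40% and 80% it is 40% and 75%.

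**Step 5: a larger effect.** At 95% against 75%, a true gain of 20 points appears as 5.4, 5.8 and 4.2 points for u = 40%, 60% and 80%, with Fisher power of 16%, 16% and 12%. The direct comparison has 90%, 98% and 99.8%.

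**Step 6: are the assumptions possible here?** Section 11.2 allows for 347 − 300 = 47 non-evaluable subjects (13.5%) and does not say how many are never-starters. Step 3 implies 173 × u × (0.05 + 0.15) never-starters in total: about 14, 21 and 28 for u = 40%, 60% and 80%. All fit within 47.

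**The case against.** **The plan never says that this test measures uptake.** This stands. Section 2.1.3 asks for a description of timing and a within-ONN analysis. A reader might infer that the trial set out to show navigation gets patients onto therapy and chose a test that fails; the documents do not support that. The valid point is that the plan specifies a between-arm p-value that no stated objective needs and that is easily misread.

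**The split is openly defined, and a check in a set selected after randomisation could flag differential selection.** This stands in part. Section 11.3.3 is clear about the binary variable, and the proportion does move when uptake differs. A reader might infer that the test can show nothing at all about uptake; that is too strong. But a shift of 2 to 3 points for a 10-point effect, mixed with chance imbalance at entry, cannot be read back as uptake, and with power this low the test is a poor selection check too.

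**Other analyses are closer to what navigators do.** This is fair. Time to initiation bears more directly on speed, and referrals and no-shows in 11.3.2 also reflect navigator work. The timing comparison, however, is itself restricted to subjects who started after randomisation.

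**The ITT set may have been meant for this step.** Section 11.5.6 does not restate its population there, but 11.4 assigns exploratory endpoints to the evaluable set and 11.3.3 has no code for never-starters. That reading would also need new text.

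**Conclusion.** The point holds for an exploratory analysis. Under 11.1.2, 11.3.3 and 11.4, the proportion tested in 11.5.6 is exactly the complement of being on therapy before randomisation. This rests on definitions alone. Its Fisher test mainly reflects chance imbalance plus a diluted selection effect, and neither a significant nor a null result can be interpreted as an effect of navigation on starting therapy. The ANOVA of time to initiation describes only those who started after randomisation.

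The size is illustrative. It depends on the assumed start rates, the assumed share untreated, a further dose for all prior starters, and no loss through the six-month criterion. On those terms a 10-point effect shrinks to about 1.9 to 2.8 points, with power of roughly 6% to 8%, against about 61% for the direct comparison at 60% untreated.

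A reader might infer that the co-primary results are compromised by this test. They are not: it carries no alpha, stopping rule or decision, and it does not enter the OS6 or acute care analyses.

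**What to change.** - **11.5.6.** Report the number and percentage already on systemic therapy at randomisation, by arm, as a description with no test. If a between-arm comparison of initiation is kept, run it among all randomised subjects not yet on systemic therapy at enrollment. Compare (a) the proportion who start, with never-starters counted as not started, and (b) time to start as cumulative incidence, with death before start as a competing event and censoring at the off-study date for other reasons. Censoring is needed because 8.2 ends data collection when a subject goes off study.
- **11.4.** Add an exception to the evaluable-population rule for this analysis.
- **11.3.3.** State how never-starters are handled, for both the time and the binary variable.

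The cost is small edits to three sections and one competing-risk analysis in place of the ANOVA. Little or no new data should be needed: 11.3.3 already needs start dates, and deciding evaluability already requires knowing whether each randomised subject received a dose after enrollment. If the team does not want a between-arm question about initiation, dropping the Fisher test and labelling the ANOVA as descriptive of on-study starters would be enough.

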2.1.3 Exploratory objectives

- To compare outcomes within the ONN arm for subjects navigated by GI specialists versus subjects navigated by general oncology nurse navigators.

- To describe the distribution of the timing from enrollment to initiation of systemic therapy.
- To evaluate outcomes within the ONN arm as a function of the time from enrollment to initiation of systemic therapy in those evaluable subjects initiating systemic therapy on study.

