11.3 Endpoints

11.3.1 Definition of Primary Endpoints

Overall survival at 6 months (OS6) will be determined as a binary variable indicating whether or not the subject was alive at 6 months following randomization.

Acute care utilization visits will be calculated for each subject as the total number of acute care visits normalized to an annual basis. Acute care visits will include unplanned hospital admissions, ED visits, and urgent care visits.

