11.3.2 Definition of Secondary Endpoints

- Overall Survival (OS)

OS is defined as the duration from enrollment to the study (randomization) to the date of death from any cause. Subjects who are alive or lost to follow-up at the time of the analysis will be censored at the last known date they were alive.

- Overall survival at 12 months (OS12) will be determined as a binary variable indicating whether or not the subject was alive at 12 months following randomization.

- Length of hospital stay (LOS)

Length of stay will be calculated for each subject and for each unplanned in-patient admission as the difference between the admission date and the discharge date (plus 1).

- Time from hospice referral to death

Time from hospice referral to death is defined as the duration from hospice referral to the date of death from any cause. Subjects who are alive or lost to follow-up at the time of the analysis will be censored at the last known date they were alive. This endpoint will only be calculated for subjects referred to hospice.

- 30-day readmission

The 30-day readmissions will be calculated for each subject as the total number 30-day readmissions. This endpoint will only be calculated for subjects with at least one in-patient admission.

- Referral to Supportive Oncology services

Referral to Supportive Oncology will be binary variables determined for each subject indicating whether or not the patient received referrals to Palliative Care, Nutrition Services, and Social Work Services offered by the Levine Cancer Institute Department of Supportive Oncology.

- Adherence to clinical care

Adherence to clinical care will be calculated for each subject in terms of the rate of subject compliance with scheduled visits. For each subject, the number of no-shows will be calculated as a percent of all scheduled within Atrium Health visits, regardless of visit type.

- Patient satisfaction

Patient satisfaction will be assessed through the EORTC IL109 customized questionnaire. The EORTC IL109 customized questionnaire was compiled in the EORTC web-based library system and combined selected items from the PATSAT-C33 and OUT-PATSAT7 questionnaires. The selected scales and individual items included in the IL109 questionnaire are shown in Table 11.3.2

Table 11.3.2 Scoring the IL109 customized questionnaire (Appendix B)

Scoring the PATSAT IL109	Number of items (n)	Item range*	item numbers (I1, I2, ..., In)
Scales			

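### The exploratory analysis of outcomes by time to systemic therapy counts survival from randomization, so later starters carry guaranteed survival time

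*Combined protocol and SAP*

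**What the plan says.** The aim is listed in section 2.1.3: "To evaluate outcomes within the ONN arm as a function of the time from enrollment to initiation of systemic therapy", among evaluable subjects who begin systemic therapy on study. Section 11.5.6 carries it out with optional wording: "Outcomes may be evaluated and compared within the ONN arm with regards to time to initiation of systemic therapy". The delay may enter as a continuous or a categorical measure, with 0 to 6 days versus 7 or more days as the example grouping. On endpoints it says: "These analyses will be conducted on the primary and secondary endpoints as described above".

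The definitions that feed this analysis are:

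- **Covariate** (11.3.3): "Time to initiation of systemic therapy will be calculated as the difference (in days) between the dates of enrollment and initiation of systemic therapy".
- **Enrollment date** (11.1.2): "The date that the subject is randomized".
- **OS** (11.3.2): "OS is defined as the duration from enrollment to the study (randomization) to the date of death from any cause".
- **OS6** (11.3.1): a "binary variable indicating whether or not the subject was alive at 6 months following randomization". OS12 is defined in the same way at 12 months (11.3.2).
- **Entry to the evaluable population** (11.4), first condition: "Receive at least one dose of standard of care systemic anti-cancer therapy on or after the enrollment date".

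The survival methods carried over from section 11.5.5 are Kaplan-Meier, log-rank and Cox regression. No landmark, delayed entry, time-dependent covariate or new time origin is specified for this analysis.

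**The concern.** The delay becomes known only after the survival clock has started, and a subject who dies before the first dose is not in the analysis set. A subject classed as a day-28 starter must have lived 28 days from enrollment; a day-3 starter needs to have lived only 3. Deaths in the waiting period are thus removed, and more of them are removed the longer the wait. This is immortal-time bias, and for OS6, OS and OS12 it pushes toward later start looking better.

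Nothing in the plan caps the wait. The 30-day limit in section 3.2 restricts how long after starting therapy a subject may enroll, not how long after enrollment therapy may start.

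ACU has a related but separate problem. Visits are collected from randomization (section 7.2), so an unplanned admission before the first dose counts as an outcome and may also be what delayed the dose.

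At stake is how the exploratory objective can be read. Expediting care is one of the navigator's tasks (section 5.1), so readers will look to this analysis for what timing has to do with outcome.

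**Working it through.** **Inputs from the documents.** Section 11.2 gives an 8-month exponential median under standard therapy, a 6-month survival of about 60%, and a design rate of 80% with navigation. The 7-day grouping is from section 11.5.6. **Assumed:** the distribution of delay, a constant hazard, and no true effect of timing.

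**1. The plan's own figure.** S(6) = exp(−ln 2 × 6/8) = 0.595, which agrees with the stated approximate 60%.

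**2. Fixed start days.** For a subject alive at start day d, with no timing effect,

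P(alive at 6 months from enrollment) = exp(−λ × (6 − d/30.44)).

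- ONN design rate of 80%: λ = −ln(0.80)/6 = 0.0372 per month. Day 3 gives 80.3% and day 28 gives 82.8%, a spurious difference of 2.5 points.
- 8-month median: λ = ln 2/8 = 0.0866 per month. Day 3 gives 60.0% and day 28 gives 64.4%, a spurious difference of 4.4 points.

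**3. The plan's example grouping.** One million subjects were simulated per scenario, with delay independent of survival. Only subjects alive at their planned start were kept, and follow-up was censored at 30 months. The table compares 7+ days with 0–6 days on the enrollment clock, as planned. Differences were taken before rounding.

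| OS6 rate | Assumed delay | OS6, 7+ days | OS6, 0–6 days | Spurious gap (points) | Spurious HR |
|---|---|---|---|---|---|
| 80% | uniform 0–28 days | 81.7% | 80.3% | 1.4 | 0.975 |
| 80% | exponential, mean 14 days | 82.0% | 80.3% | 1.7 | 0.972 |
| 80% | exponential, mean 30 days | 83.6% | 80.3% | 3.4 | 0.941 |
| 80% | uniform 0–90 days | 84.9% | 80.3% | 4.5 | 0.924 |
| 60% | uniform 0–28 days | 63.0% | 60.5% | 2.5 | 0.956 |
| 60% | exponential, mean 14 days | 63.4% | 60.4% | 3.0 | 0.948 |
| 60% | exponential, mean 30 days | 66.2% | 60.4% | 5.8 | 0.909 |
| 60% | uniform 0–90 days | 68.6% | 60.4% | 8.1 | 0.877 |

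**4. Does the remedy work?** In the same eight scenarios the HR was 0.998 to 1.004 with delayed entry at the first dose, and 0.998 to 1.004 with the clock started at the first dose. Both remove the bias.

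**5. Follow-up after a change of clock.** Evaluability secures survival status only to 6 months from enrollment. For a day-28 starter that is 6 − 28/30.44 = 5.08 months from the first dose. A binary 6-month status from the first dose could therefore be missing for some subjects, which is why Kaplan-Meier is needed.

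No figure was derived for ACU; that part rests on the definitions alone.

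**The case against.** The strongest reply is that this matters little. The analysis is exploratory, within one arm, non-randomized and optional, and no decision rule depends on it. It is confined to the ONN arm, so the 80% design rate is the more relevant hazard. There, the plan's example split with short delays gives only 1.4 to 1.7 points. The entry criterion of life expectancy above 3 months should thin out early deaths, which are the source of the bias. Sampling error is also larger: with 150 evaluable subjects in the arm, a 75/75 split at 80% has a standard error of √(0.8 × 0.2 × 2/75) = 6.5 points, a 95% half-width near 13. All of this stands, and it limits the weight of the point. It does not remove a bias of known direction, which grows once delays reach a month or more.

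A second objection is that restarting the clock discards the interval from randomization to first dose, when navigation is already under way (section 5.2). That is a fair cost. Delayed entry avoids changing the time origin for OS.

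A reader might infer that the plan sets out to show earlier treatment is better, and that the bias would hide or reverse a true benefit. The documents do not support this. Section 2.1.3 names no direction, and no true effect size is given against which to judge a reversal. Nor does it follow that delay will look protective in the data: sicker patients may start earlier or later, and that confounding could move the result either way.

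**Conclusion.** The point holds as a flaw in one exploratory analysis. Following section 11.5.6 as written builds guaranteed survival time into the later-start group for OS6, OS and OS12. The bias favors later start. Its size depends on an undocumented delay distribution: about 1.4 to 3.0 OS6 points for the 7-day split with short assumed delays, and 3.4 to 8.1 with longer ones, across OS6 rates of 80% and 60%. The 4.4-point day-28 versus day-3 figure uses the standard-therapy hazard and should not be read as the expected bias in the ONN arm, where the design rate gives 2.5. These figures assume a constant hazard and no true timing effect.

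A reader might also extend the criticism to the trial's main result. That is not supported: the delay covariate is used only within the ONN arm and does not enter the randomized comparison of the co-primary endpoints.

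**What to change.** Amend section 11.5.6 for this objective only:

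- **OS:** use Cox regression with delayed entry at the first dose, keeping the randomization clock, or start the clock at the first dose. In either case use days from enrollment to initiation as a covariate.
- **6- and 12-month survival:** estimate from the first dose by Kaplan-Meier, in place of a binary OS6.
- **ACU:** count visits and exposure time from the first dose.
- **Reporting:** say that the association remains open to confounding.

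The cost is SAP wording. The enrollment and initiation dates are already needed for the endpoint in section 11.3.3, and section 7.2 tracks hospital admission dates. The sponsor should confirm that dates of emergency and urgent care visits are also recorded. The downside is a time zero that differs from the main analysis wherever the clock is restarted, and the omission of ACU between randomization and first dose from this exploratory analysis. The main analyses stay as they are.
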